11.3.3 Baseline Analysis and Covariate Adjustment

With minimization randomization, we do not expect groups differences in the distributions of potentially prognostic baseline variables. We will check for imbalances in other baseline variables not used in minimization including childhood trauma and objective measures of total sleep time (sleep duration), wake after sleep onset (sleep continuity) and sleep quality (PSQI) assessed prior to baseline and include them as covariates in the analyses as needed. To explore how much of the change in amygdala reactivity and traumatic symptom reductions are associated with an improvement in sleep, we will also include separately each potential intermediate outcomes of the weekly average of total sleep time, wake after sleep onset and sleep quality assessed prior to each study visit (Days 22, 36) as predictors of outcomes. We will also explore if diagnostic status (baseline SCID) moderates the treatment response.

12 Supporting Documentation & Oversight Considerations

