7.4 Measures to Minimize Bias

7.4.1 Randomization

Participants will be randomized at Visit 3, after the week-long baseline period, to one of 3 daily light durations (15, 30 or 60 minutes/day) using a secure web-based treatment assignment system implemented by CSCAR (cascar-randomization.appspot.com). This system uses a minimization approach to reduce imbalances in covariates following each round of treatment assignment by using non-uniform assignment probabilities for the different treatment groups. The following minimization variables will be used: combat vs. non-combat index trauma; DASS; use of psychoactive medication; ages, sex and race.

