11 STATISTICAL CONSIDERATIONS

11.1 GENERAL APPROACH

The objective of this study is to establish a signification dose response relationship between the duration of morning light treatment and reduction in amygdala reactivity from baseline to treatment week 2 (study week 3) and/or treatment week 4 (study week 5).

Statistical analyses will include intent-to-treat and completer analysis. Data will be analyzed using responses at all three times (baseline, 2 [when data available] and 4 weeks) as dependent variables using a mixed-effects longitudinal model [106, 107] with participants as random intercepts to account for between participant variability and time as a predictor.

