11.2 ANALYSIS OF PRIMARY OUTCOME

We will first graphically explore the relationship between responses and dose by time and specify how dose and time will be parameterized. For example, if a linear dose-dependent relationship is shown at each follow-up time (e.g., incremental drop in amygdala reactivity with increasing duration of daily light pulse), we will assess it by including dose (in minutes) and will include the interactions of time by dose to assess how/if the relationship changes over time (e.g., no difference across groups at baseline and dose-dependent relationship at weeks 2 and 4). A test of overall dose response relationship between duration of daily light pulse and reduction from baseline in amygdala reactivity will be established based on the significance of the interaction term. Time can also be included as categorical indicators to see, for example, if 4 weeks, relative to 2 weeks achieve even greater (or no greater) response.

If a nonlinear dose-dependent relationship is shown in graphs, it will be explored using indicators of dose groups. If the relationships at 2 weeks differ from those at 4 weeks, we will analyze them using separate models.

Statistical analysis will be performed using SAS 9.3. Regarding missing data, if "non-ignorable" patterns are detected, then "pattern mixture", "selection models", or other appropriate strategies will be used to examine the impact of the missing data pattern on the key outcomes [108, 109]. All analyses will include tests for sex differences, in order to examine sex as a biological variable.

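### Six minimisation factors are left out of the primary dose-by-time model, apart from unspecified sex tests. Pre-specifying them with factor-by-time terms is a cheap, low-severity gain in efficiency.

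*Combined protocol and SAP*

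**What the plan says.** Section 7.4.1 (Randomization) describes minimisation with non-uniform assignment probabilities: "The following minimization variables will be used: combat vs. non-combat index trauma; DASS; use of psychoactive medication; ages, sex and race".

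Section 11.1 sets out a mixed-effects longitudinal model "with participants as random intercepts to account for between participant variability and time as a predictor". Section 11.2 adds dose and its interaction with time, and the dose response "will be established based on the significance of the interaction term". The only minimisation factor mentioned in the analysis is sex, with no model term given: "All analyses will include tests for sex differences, in order to examine sex as a biological variable".

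Section 11.2 does not fix the dose form. The data are graphed first and dose is entered in minutes if the pattern looks linear. Otherwise: "If a nonlinear dose-dependent relationship is shown in graphs, it will be explored using indicators of dose groups".

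Section 11.3.3 says that, because of minimisation, "we do not expect groups differences in the distributions of potentially prognostic baseline variables". It then turns to the remaining variables: "We will check for imbalances in other baseline variables not used in minimization". These are childhood trauma and sleep measures, and the plan is to "include them as covariates in the analyses as needed". No section adds the six minimisation factors to the primary model.

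**The concern.** Section 11.3.3 in effect treats expected balance as the reason not to adjust. Under minimisation, balance on a factor that predicts the outcome removes that factor's contribution to chance differences between arms. The true sampling variation of the dose effect therefore shrinks. A model that omits the factor still counts its variation as residual error and reports a standard error that is too large.

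For this trial the relevant outcome is change. A factor that predicts only the level of amygdala reactivity does no harm, because the participant intercept absorbs it. A factor that predicts change matters, because the test is a dose-by-time interaction.

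What is at stake is efficiency in the test that answers the stated aim (section 4) and hypothesis (section 11.1.1), a significant dose response, in a trial planning to enrol 66 people (section 6).

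**Working it through.** **Inputs from the documents.** 66 participants; three arms at 15, 30 and 60 minutes; six minimisation factors; scans at visits 3 and 7, with visit 5 scans only for earlier participants (section 9.7). There is no power calculation to reproduce.

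**Assumptions.** Two-sided 5% level; 22 per arm; 80% probability for the preferred arm; six binary factors with equal weights; R² for change of 0 to 0.3; a difference of 0.8 SD of change between 60 and 15 minutes. None of these is stated in the documents.

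**Step 1. Reduce the test.** With two complete scans, the dose-by-time test in a random-intercept model equals least squares of change on dose.

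**Step 2. Standard error reported by the planned model.** The mean dose is 35, so the deviations are −20, −5 and +25. The sum of squares is 22 × (400 + 25 + 625) = 23,100. In SD units of change, the SE of the 60 v 15 difference is 45/√23,100 = 0.296. Then 0.8/0.296 = 2.70, which gives power of 76% at R² = 0 (noncentral t, 64 df).

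**Step 3. True sampling SD under minimisation.** With perfect balance it would be 0.296 × √(1 − R²), or 0.248 at R² = 0.3. Minimisation with 80% preferred assignment is less complete: at R² = 0.3 a simulation gave a true SD of 0.262 against a mean reported SE of 0.295. With the factors in the model the two agree (0.251 and 0.250).

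**Step 4. Simulation, 20,000 trials per cell, linear dose, 66 analysed.** Simulation error is about 0.15 points on type I error and 0.3 on power.

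| Assumed R² | Reported SE / true SD, without factors | Type I, without | Type I, with | Power, without | Power, with |
|---|---|---|---|---|---|
| 0 | 1.001 | 4.9% | 4.8% | 75.7% | 74.6% |
| 0.1 | 1.045 | 4.1% | 5.0% | 76.9% | 79.2% |
| 0.2 | 1.093 | 3.4% | 5.1% | 77.5% | 83.5% |
| 0.3 | 1.145 | 2.4% | 5.0% | 78.5% | 88.0% |

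As a hand check, 2 × [1 − Φ(1.96 × ratio)] with the ratios in the second column gives 5.0, 4.1, 3.2 and 2.5%.

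**Step 5. Sensitivity at R² = 0.3.**
- Preferred-arm probability 1.0 or 0.6 (2,500 trials each): unadjusted type I error 2.2% or 3.2%.
- Adjusting for sex only: type I error 2.7%, power 80%.
- Dose-group indicators (2 df), without v with the factors: type I error 2.0 v 5.0%, power 65 v 80%.
- Week-2 scan in an assumed third, random-intercept REML model: type I error 3.3 v 5.3%, power 81 v 88%.
- Simple randomisation: type I error 5.4 v 5.2%, power 75 v 85%.

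The last line separates two effects. The conservatism comes from minimisation. The power gain of about 10 points appears under simple randomisation too, so it is ordinary covariate adjustment.

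**Step 6. Which terms help.** In a mixed model fitted to one simulated data set, adding sex and medication as main effects left the interaction SE at 0.00729. Adding them as factor-by-time terms reduced it to 0.00618.

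**Step 7. The choice of dose form.** As an upper bound on choosing between the linear and dose-group forms, I took the smaller of the two p-values. Unadjusted type I error was then 8.0, 6.4, 5.1 and 3.9% at R² 0, 0.1, 0.2 and 0.3.

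**The case against.** The strongest reply is that the whole effect depends on an R² the documents do not supply. At R² = 0 adjustment loses a little power, and at 0.1 it gains about 2 points. Some factors may carry little information: section 6.2 excludes several classes of psychoactive drug, and much of the recruitment is from the community (section 6.4), so combat trauma may be sparse. That stands. The sponsor did choose these variables for balancing, but that does not show that they predict change in BOLD signal.

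A reader might infer more than the documents support, in three ways:

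- **That the primary test as planned runs below 5%.** No level is stated for it, and section 11.2 picks the dose form from graphs. The smaller-p bound in step 7 exceeds 5% at R² of 0 and 0.1 and is about 5% at 0.2. It does not cover the further option of separate models by week. Conservatism is therefore shown only for a dose form fixed in advance.
- **That the omission threatens validity.** It does not. Leaving the factors out creates no false positives, and unadjusted power does not fall as R² rises (75.7 to 78.5%).
- **That the go/no-go decision is at risk.** Section 11.1.2 uses an effect size of at least 0.5 in one arm and not this p-value.

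The simulations used binary factors, apart from a variant with four race categories. Section 7.4.1 does not say how DASS and age enter the algorithm, so the figures are untested for continuous versions of those two.

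**Conclusion.** The point holds as a low-severity efficiency improvement. The plan allocates on six factors and leaves them out of the primary model, apart from unspecified sex tests. If they explain 20 to 30% of the variance in change, a pre-fixed test at an assumed 5% level rejects a true null about 2.5 to 3% of the time, and adjustment adds about 6 to 10 points of power. At 10% the effect is small, and at zero there is nothing to gain. Only the conservatism is specific to minimisation. The size rests on the assumed R², 0.8 SD difference, assignment probability and factor coding.

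**What to change.** In the primary mixed model, pre-specify the six minimisation factors with factor-by-time terms. Alternatively, use a baseline-adjusted change model with the six factors as covariates. Main effects alone are not enough: with two complete scans they leave the dose-by-time test unchanged.

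Enter DASS and age as continuous covariates, or in the form the allocation algorithm uses. Enter race in the algorithm's categories, collapsing sparse ones by a rule fixed in advance. Do the same in the symptom models of section 11.3.2, without entering baseline DASS twice when DASS is the outcome.

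The cost is SAP wording and about 6 to 8 degrees of freedom: six binary factors take 6, and four race categories bring it to 8. If no factor predicts change, power falls by 1 to 2 points with 66 analysed (75.7 to 74.6% with binary factors; 75.8 to 73.6% with four race categories). With an assumed 54 analysed it falls by 2 to 4 points (66.7 to 64.6%; 67.0 to 63.5%; 56.0 to 52.2% for the dose-group test with four race categories).

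### The exploratory sleep analysis in section 11.3.3 asks about improvement in sleep but enters sleep levels, so its coefficient mixes stable differences between people with change within a person

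*Combined protocol and SAP*

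**What the plan says.** Section 11.3.3, under the exploratory analyses, states its purpose: "To explore how much of the change in amygdala reactivity and traumatic symptom reductions are associated with an improvement in sleep". The predictors follow: "we will also include separately each potential intermediate outcomes of the weekly average of total sleep time, wake after sleep onset and sleep quality", each "assessed prior to each study visit (Days 22, 36) as predictors of outcomes". Day 8, the baseline visit, is not in that list.

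Baseline sleep appears earlier in the same paragraph for a different purpose. The arms are checked for imbalance in childhood trauma and in sleep measures "assessed prior to baseline and include them as covariates in the analyses as needed".

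The model is the one in section 11.1: "Data will be analyzed using responses at all three times (baseline, 2 [when data available] and 4 weeks) as dependent variables", in a "mixed-effects longitudinal model [106, 107] with participants as random intercepts to account for between participant variability and time as a predictor". The plan does not specify a change from baseline in sleep, a centring of sleep within person, or a baseline-sleep term that is always present.

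**The concern.** An improvement cannot be read from a level alone. Suppose that people who habitually sleep badly also have higher amygdala reactivity, and that nobody's reactivity follows a change in their sleep. A random intercept does not remove that stable association from the coefficient of a time-varying predictor, so the sleep term can be significant although the true answer to the stated question is no. The reverse can also happen: a real within-person link is diluted, or offset by a between-person association of opposite sign.

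The conditional baseline-sleep covariate does not reliably repair this. It is triggered by imbalance between arms, and perfectly balanced arms leave the between-person association intact. At stake is whether a reported sleep link, or its absence, means what section 11.3.3 says it would mean.

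**Working it through.** The plan gives no power or error figure for this analysis, so there is none to reproduce.

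**Inputs from the documents.** 66 participants (section 6); scans at Visits 3 and 7 only under the current plan (section 9.7); three arms; outcome levels with a random intercept (section 11.1); baseline-week actigraphy and a Visit 3 PSQI (sections 1.3 and 7.3).

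**Assumptions, not in the documents.** Intraclass correlation (ICC) of weekly sleep 0.6-0.8 and of reactivity 0.3-0.5 (one run used 0.7 for both); correlation r of the stable parts 0 to 0.5; two-sided 5% test; no true within-person link unless stated.

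**1. What one level coefficient estimates.** Scale sleep S and reactivity Y to unit variance. With two visits, the random-intercept estimate is close to a weighted mean of the between-person slope b_B and the within-person slope b_W:

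b = (w_B·b_B + w_W·b_W) / (w_B + w_W), with w_B = Var(mean S) / residual Var(mean Y) and w_W = (1 − ICC_S) / (1 − ICC_Y).

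Take ICC_S = 0.6, ICC_Y = 0.5, r = 0.5, b_W = 0:
- trait covariance = 0.5·√(0.6·0.5) = 0.274
- Var(mean S) = 0.6 + 0.4/2 = 0.8, so b_B = 0.274/0.8 = 0.342
- residual Var(mean Y) = 0.75 − 0.342·0.274 = 0.656
- w_B = 0.8/0.656 = 1.219 and w_W = 0.4/0.5 = 0.8
- b = 1.219·0.342/2.019 = 0.207
- SE = 1/√(66·2.019) = 0.087, z = 2.39, rejection about Φ(2.39 − 1.96) = 66%

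Simulation of the same setting (REML, time, dose and time-by-dose in the model, 1,500 runs) gives b = 0.211 and 64%. At r = 0.3 the formula gives b = 0.120 and 27%; simulation gives 0.122 and 27%. The true within-person slope is zero throughout.

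**2. Dependence on how the sentence is read.** Same simulation, ICC_S 0.6, ICC_Y 0.5, rejection rate with no within-person link:

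| Reading | r = 0.3 | r = 0.5 |
|---|---|---|
| Sleep level at every visit, baseline included | 27% | 64% |
| Follow-up level held constant per person | 34% | 75% |
| Baseline rows dropped (cross-sectional at follow-up) | 26% | 61% |
| Baseline outcome rows kept, sleep term acting on follow-up rows only | 11% | 27% |
| Change in outcome on follow-up level | 4% | 6% |
| Level at every visit plus baseline sleep | 6% | 11% |
| Change on change, or person-mean split | 4% | 6% |

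**3. Dependence on the trait correlation.** A separate simulation of the first row gives 5-6% at r = 0, about 14% at 0.2, 26-32% at 0.3 and 64-68% at 0.5. Over all ICC pairs tried, the rate at r = 0.5 runs from 52% to 79%.

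**4. Missed links.** If change in outcome is regressed on the Day 36 level, the expected slope is the true one multiplied by Cov(S36, S36 − S8)/Var(S36) = 1 − ICC_S. At ICC_S = 0.6 that is 0.4; the simulated slopes give 0.184/0.451 = 0.41. With a within-person correlation of 0.4 and r = 0, power is 31% for the level against 94% for change in sleep. In the mixed model, the level at every visit has 84%. If the trait correlation has the opposite sign (−0.4), that falls to 27%, against 92% for change in sleep.

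**The case against.** The strongest reply is that this is one exploratory sentence. It carries no hypothesis, significance level or decision rule, and section 9.4 describes the sleep measures as compliance indices and covariates. That stands. A reader might infer that this is the trial's main check of mechanism and that the interpretation of the dose response hangs on it. The documents do not support that: section 2.1 rests the rationale on direct and indirect light pathways to the amygdala, and the objective, hypothesis, go/no-go rule and primary test make no use of sleep.

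Second, the aim is worded in terms of change and symptom reductions, so a change-score outcome is a plausible reading, and it yields no false link. That also stands, but the loss of power in step 4 remains.

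Third, it would be too strong to say that a level term cannot detect improvement. Entered at every visit, it has 84% power when there is no trait correlation.

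Fourth, the question is how much, and the sleep coefficient is not the same as the attenuation of dose-by-time. Randomisation balances traits across arms: in simulation the mean attenuation was 0.000 when light did not shift sleep. Bias appeared when light was assumed to shift sleep: 0.06 of a true 0.30 (20%) in one run with a 0.3 SD shift per dose step. This limits the damage to dose-by-time, but not to statements about the sleep coefficient itself.

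**Conclusion.** The mismatch between question and predictor is on the page, and the specified model does not resolve it. Its size is uncertain. It is negligible if habitual sleep and stable reactivity are nearly uncorrelated between people (6-7% false links at r = 0.1), and large at r = 0.3 or above if sleep enters as a level at every visit. No document gives r or the ICCs, so the rates in steps 2 and 3 are conditional on those assumptions. Under a change-score outcome only power is lost.

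The dose-by-time test of section 11.2 and the go/no-go rule of section 11.1.2 are not affected. Severity is minor, because the analysis is exploratory.

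**What to change.** In section 11.3.3, for each sleep measure, use the baseline-week value as well as the follow-up values, and specify one of:

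- (a) in the mixed model, two terms: the person's mean sleep over visits and the deviation from that mean at each visit; or
- (b) a regression of change in outcome on change in sleep from the baseline week.

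State that only the within-person (change) coefficient is read as improvement in sleep. For the how-much question, report the dose-by-time estimate with and without that term. With scans at Visits 3 and 7 only, (a) and (b) give practically the same answer for reactivity; symptoms also have Day 22.

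Making baseline sleep a permanent covariate beside the level is better than the present text, but it still left 6-11% false links where a trait correlation was assumed, against 4-6% for (a) or (b).

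The cost is SAP wording and one extra term per model. Baseline-week actigraphy and the Visit 3 PSQI are already collected.

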12.1 REGULATORY, ETHICAL & STUDY OVERSIGHT

12.1.1 Informed Consent Process

The recruitment and informed consent process is designed to provide information about study participation multiple times and in different formats. Individuals expressing interest will be provided with a verbal explanation of study procedures and the risk-benefit profile and/or be able to read basic study information on the umhealthresearch.org website. From there, individuals are provided with an IRB-approved copy of the consent document to review at their leisure.

The informed consent dialog will take place at the initial study visit (Day 0). It will consist of a dialog between the study team and the potential participant. The discussion will focus on the voluntary nature

of research, expectations for participation, a discussion of the risks and benefits associated with being in the study, the difference between research and clinical care, and include time for questions.

The physical location for the consent dialog will be private research space within the Sleep and Circadian Research Laboratory.

12.2 DATA RETENTION

Research data will be retained for both study record-keeping purposes and for future unspecified research use according to IRBMED guidelines for federally-funded projects. All paper and computer records will be identified by the subject ID code rather than name or other identifier. Consent documents and other forms with identifiers will be stored in a separate double-locked setting.

Data from participants who withdraw from the study will be retained in the study database.

12.2.1 Study-record keeping

Hard copies of the data will be maintained for 7 years after which they will be destroyed. Files will be stored in double-locked environment and access-limited under the purview of the MPIs. All research records will be identified by subject ID; pre-screening records will be scrubbed of identifiers and date shifted to preserve confidentiality.

Study database records will be identified by subject ID, and the link between identifiers and subject ID will be maintained by the MPI, [name], and lab manager. The link will be destroyed after submission of the NIH final report for Phase 2 (R33) if funded, or publication of the primary manuscript for Phase 2, whichever is later. If Phase 2 is not funded, then the link will be destroyed after submission of the final NIH report for this study (Phase 1 – R61).

12.2.1.1 Protected Health Information (PHI)

We will abstract basic eligibility and contact information from the Michigan Medicine electronic medical records system, MiChart. These data will be stored separately from study data and will be retained with identifiers throughout the duration of the study. Once the study concludes, the identifiers will be destroyed.

